#### 7.4 Statistical Analysis Plan

All computations and statistical analyses of the data will be performed by CPT using Microsoft Excel 365 (2021) and will be reviewed by the Quality Assurance Department internally at CPT. Since all statistical methods are specified in this protocol and they are all in accordance with ISO 24444: 2010 (E), a separate Reporting Analysis Plan (RAP) will not be created for this trial.

A listing with all the individual subject results will be tabulated along with summary statistics, including the average SPF, the number of valid pieces of data used to calculate the average, the standard deviation, the standard error of the mean, the critical t-value from a 2-sided Student's t-distribution, the c value (or t value X SEM), the upper and lower 95% Confidence Interval bounds, and the Confidence Interval percentage (or CI[%]) on the mean SPF (see Section 7.3 for details on calculation). A passed or failed grade will also be provided in the listing. Excluded subjects will be flagged accordingly, and reasons for exclusion will be provided in the listing.

## 8 Adverse Event and Serious Adverse Events

The investigator and any qualified designees are responsible for detecting, documenting, and reporting events that meet the definition of an AE or SAE and remain responsible for following up AEs that are serious, considered related to the trial product or the trial, or that caused the subject to discontinue the trial product or trial.

### 8.1 Definition of an Adverse Event (AE)

An AE is any untoward medical occurrence in a clinical trial subject, temporally associated with the use of a trial product including any washout or lead-in product (or medical device), whether or not considered related to the trial product, including any washout or lead-in product (or medical device).

NOTE: An AE can therefore be any unfavorable and unintended sign (including an abnormal laboratory finding), symptom, or disease (new or exacerbated) temporally associated with the use of a trial product including any washout or lead-in product (or medical device).

#### Events Meeting the AE Definition:

- Unexpected or unusual reactions which occur within the test area that cannot be completely described by the scale in 6.2.2.(e.g., hives) will be recorded as AEs.
- Any abnormal laboratory test results (hematology, clinical chemistry, or urinalysis) or other safety assessments (e.g., ECG, radiological scans, vital sign measurements), including those that worsen from baseline, considered clinically significant in the medical and scientific judgment of the investigator (i.e., not related to progression of underlying disease).
- Exacerbation of a chronic or intermittent pre-existing condition including either an increase in frequency and/or intensity of the condition.
- New conditions detected or diagnosed after trial product administration even though it may have been present before the start of the trial.
- Signs, symptoms, or the clinical sequelae of a suspected drug-drug interaction.
- Signs, symptoms, or the clinical sequelae of a suspected overdose of either trial product or a concomitant medication. Overdose per se will not be reported as an AE/SAE unless it is an intentional overdose taken with possible suicidal/self-harming intent. Such overdoses should be reported regardless of sequelae.
- "Lack of efficacy" or "failure of expected pharmacological action" per se will not be reported as an AE. Such instances will be captured in the efficacy assessments. However, the signs, symptoms, and/or clinical sequelae resulting from lack of efficacy will be reported as AE if they fulfill the definition of an AE.

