## 6.2 Determination of Minimal Erythral Dose (MEDu)

### 6.2.1 Methodology

Within 1 week prior to the test material phase, a provisional MEDu of each subject shall be determined by a progressive sequence of timed UV radiation exposures, each of which shall be graduated incrementally by 25% over that of the previous exposure. The test sites shall be evaluated for erythema according to the MED Scoring Scale (Section 6.2.2). The MED is the lowest dose of UVR that produces the first perceptible unambiguous erythema with defined borders appearing over most of the field of UV exposure, 16 h to 24 h after UV exposure (Score of 1 or greater on the MED Scoring Scale).

On the same day as the test material is irradiated, an MEDu shall be determined by a progressive sequence of timed UV radiation exposures. The exposures shall be graduated incrementally by 25% over that of the previous exposure, and the graduation must be consistent with that of the MEDp test sites. Further, the MEDu test site must be in close proximity to the MEDp test sites. The Test sites shall be evaluated for erythema according to the MED Scoring Scale (Section 6.2.2). The MED is the lowest dose of UVR that produces the first perceptible unambiguous erythema with defined borders appearing over most of the field of UV exposure, 16 h to 24 h after UV exposure (Score of 1 or greater on the MED Scoring Scale).

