### 6.2.2 MED Scoring Scale

Score	Description
0	No reaction
0.5	Equivocal reaction, barely perceptible erythema with no clearly defined border
1	Mild but definite erythema with clearly defined borders
2	Moderate clearly defined erythema
3	Strong erythema, edema
4	Bulla or vesiculation

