#### CONFIDENTIAL

This document is a confidential communication of Consumer Product Testing Company, Inc. containing Testing Facility capabilities and processes, and as such, is intended solely for the use of the Sponsor and Testing Facility in the performance of services. The confidential information contained herein, shall only be released by either Party upon compelled disclosure in compliance with legal or regulatory requirement.

- The disease/disorder being studied or expected progression, signs, or symptoms of the disease/disorder being studied, unless more severe than expected for the subject's condition.
- Medical or surgical procedure (e.g., endoscopy, appendectomy) is not the AE. The condition that leads to the procedure is an AE (e.g., appendicitis).
- Situations where an untoward medical occurrence did not occur (social and/or convenience admission to a hospital).
- Anticipated day-to-day fluctuations of pre-existing disease(s) or condition(s) present or detected at the start of the trial that do not worsen.
- Localized erythema caused by exposure of the skin to UV radiation is expected and will not be reported as an adverse event.

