## 8.2 Definition of a Serious Adverse Event (SAE)

A Serious Adverse Event (SAE) is a particular category of an adverse event where the adverse outcome is serious. If an event is not an AE per definition above, then it cannot be an SAE even if serious conditions are met (e.g., hospitalization for signs/symptoms of the disease under trial, death due to progression of disease).

A serious adverse event is any untoward medical occurrence at any dose that:

- **Results in death**
- **Is life-threatening**
  - The term 'life-threatening' in the definition of 'serious' refers to an event in which the subject was at risk of death at the time of the event. It does not refer to an event, which hypothetically might have caused death, if it were more severe;
- **Requires inpatient hospitalization or prolongation of existing hospitalization**
  - In general, hospitalization signifies that the subject has been detained (usually involving at least an overnight stay) at the hospital or emergency ward for observation and/or treatment that would not have been appropriate in the physician's office or outpatient setting. Complications that occur during hospitalization are AEs. If a complication prolongs hospitalization or fulfills any other serious criteria, the event is serious. When in doubt as to whether "hospitalization" occurred, or was necessary, the AE should be considered serious.
  - Hospitalization for elective treatment of a pre-existing condition that did not worsen from baseline is not considered an AE.
- **Results in persistent or significant disability/incapacity**
  - The term disability means a substantial disruption of a person's ability to conduct normal life functions.
  - This definition is not intended to include experiences of relatively minor medical significance such as uncomplicated headache, nausea, vomiting, diarrhea, influenza, and accidental trauma (e.g., sprained ankle) which may interfere with or prevent everyday life functions but do not constitute a substantial disruption.
- **Results in congenital anomaly/birth defect**

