### **8.3 Time Period and Frequency for Collecting AE and SAE Information**

All AEs, and therefore all SAEs will be collected immediately after a subject provides consent to participate in the trial by the completion (signature) of the ICF and until 14 days following last administration of the trial product (or last procedure).

Medical occurrences that began before obtaining informed consent will be recorded in the Medical History/Current Medical Conditions section of the CRF not the AE section.

Details recorded by the subject on a diary or similar document that meet the definition of an AE must also be discussed with the subjects and transcribed in the AE section of the CRF.

All SAEs will be recorded and reported to the sponsor or designee immediately and under no circumstance should this exceed 24 hours. The investigator will submit any updated SAE data to the sponsor within 24 hours of it being available.

Investigators are not obligated to actively seek AEs or SAEs after the conclusion of the trial participation. However, if the investigator learns of any SAE, including a death, at any time after a subject has been discharged from the trial, and he/she considers the event to be reasonably related to the trial product or trial participation, the investigator must promptly notify the sponsor.

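### Does the test-area bullet in Section 8.1 keep edema and blistering (MED scores 3 and 4) out of adverse event recording?

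*Combined protocol and SAP*

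**What the plan says.** Four pieces of text decide how a local skin reaction is classified.

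- **Section 8.1, general definition.** An AE is "any untoward medical occurrence in a clinical trial subject, temporally associated with the use of a trial product", whether or not it is thought to be related. A note extends this to unfavorable and unintended signs.
- **Section 8.1, list of events that meet the definition.** One bullet is specific to the test area: "Unexpected or unusual reactions which occur within the test area that cannot be completely described by the scale in 6.2.2". Hives are the only example.
- **Section 8.1, list of events that do not meet the definition.** One entry concerns UV: "Localized erythema caused by exposure of the skin to UV radiation is expected and will not be reported as an adverse event".
- **Section 6.2.2, MED scale.** Score 3 reads "Strong erythema, edema" and score 4 reads "Bulla or vesiculation".

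Three further provisions bear on the consequences. Section 8.2 says: "If an event is not an AE per definition above, then it cannot be an SAE even if serious conditions are met". Section 6.2.1 adds an exposure series before any product is applied: "Within 1 week prior to the test material phase, a provisional MEDu of each subject shall be determined". Section 8.3 sets the start of collection: "All AEs, and therefore all SAEs will be collected immediately after a subject provides consent to participate in the trial".

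**The concern.** The test-area bullet is qualified by whether the scale can describe the reaction. A blister is on the scale, so it falls outside the bullet. One may then ask what the qualifier is for, unless on-scale reactions are to be handled differently. A technician who has entered a 4 might conclude that the scale has dealt with the matter and leave the AE page blank.

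On that reading, the worst local reactions to a deliberate UV exposure would be held only as MED scores. They would receive no intensity grade (8.5.1), no causality assessment (8.5.2) and no follow-up as AEs (8.6), and under Section 8.2 they could not become SAEs. The contents list for the final report in Section 11.8 names MEDs, SPFi values and adverse events but not subsite scores.

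The provisional MEDu series seemed to widen the gap. It is run on unprotected skin up to 1 week before the test materials are used, whereas the general definition speaks of use of a trial product.

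**Working it through.** The question is one of wording, and the plan has no figure of its own to reproduce. I set each grade of the scale against the three parts of Section 8.1.

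| Score | Finding | Caught by the test-area bullet? | Exempt as localized erythema? | Within the general definition? |
|---|---|---|---|---|
| 0 | none | no | not needed | no |
| 0.5, 1, 2 | erythema only | no | yes | removed by the exemption |
| 3 | strong erythema with edema | no | the erythema, not the edema | yes, for the edema |
| 4 | blistering | no | no | yes |
| off scale | e.g. hives | yes | no | yes |

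**Step 1: what the bullet does.** It is one entry in a list of events that count. Exclusions have a separate list. The bullet does not say that only such reactions count, so failing to meet it does not remove an event from the general definition.

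**Step 2: what the qualifier is for.** Hives have no score. Without the bullet there would be no obvious place on the scoring form for them. The qualifier can therefore serve simply to send unscored reactions to the AE page, without making scored reactions non-AEs.

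**Step 3: what is exempt.** Only localized erythema is. Edema and blistering are not named. The MED is read at a score of 1 or more (6.3.3), so scores 3 and 4 lie above the response the series is meant to find and can fairly be called unfavorable and unintended.

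**Step 4: protected sites.** The last bullet of the inclusion list says that signs and sequelae of failed efficacy are reported as AEs if they meet the definition. It carries no scale qualifier. A blister under a film that failed to protect fits it.

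**Step 5: unprotected and provisional sites.** Collection starts at consent, before any product is applied, and Section 8.3 ends it by reference to the last product administration or the last procedure. Section 8 (opening paragraph) and Section 8.4 provide for events related to the trial or to a trial procedure, and Section 8.4.2 asks for the relationship to the procedure where appropriate. In the Definitions, the test area is a region of the back and a test site includes the one used for the unprotected MED; neither is tied to product. The section as a whole expects procedure-related events.

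**Step 6: exposure multiples.** Section 6.3.2 gives 6 subsites and a step of 1.25. If the MED is at subsite k, the top dose divided by the MED is 1.25^(6−k). A valid series must have a negative subsite (7.1), so k runs from 2 to 6:

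- k = 2: 1.25^4 = 2.44
- k = 3: 1.25^3 = 1.95
- k = 4: 1.25^2 = 1.56
- k = 5: 1.25
- k = 6: 1.00

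The figure of 2.44 is not a ceiling for safety purposes. AE recording does not depend on a series being valid for SPF. In a rejected series with all six subsites positive, the MED is at or below the first dose, so the ratio is at least 1.25^5 = 3.05. Section 6.2.1 gives no subsite count for the provisional series, so neither figure applies there. The documents do not link any of these multiples to edema or blistering, so the arithmetic cannot size the concern.

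**The case for a change.** The strongest reply is that a general definition is a weak safeguard when a specific bullet points elsewhere. Staff at the reading work from the specific text, and two of them could treat the same blister differently. AE status carries real consequences in grading, causality and follow-up, and one or two sentences would remove the doubt at almost no cost.

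Part of this stands. No sentence states the AE status of scores 3 and 4, and uneven recording is possible. A clarifying line would do no harm if the section were being revised anyway.

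The rest is weaker. Uneven recording needs a negative inference that the text does not require, and the SAE consequence arises only after that inference has been made. Nor can it be said that such a reaction would go unreported. The scores are entered on the CRF, Section 9 has all data on subjects' experience go to the sponsor, and Section 11.8 ends by importing reporting items from a standard that is not among the documents. The literal tie to a trial product in the general definition is a loose phrase, but Sections 8.3, 8.4 and 8.4.2 show the intended scope.

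**Conclusion.** The concern does not call for a change. Followed as written, Section 8.1 already makes edema and blistering adverse events: the definition reaches them, the exemption does not, and the test-area bullet adds to the definition without narrowing it. What is left is a missing detail that a medically qualified investigator would fill in the same direction.

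The effect on the SPF, the 95% confidence interval, the ±17.0% criterion and the sample size is nil. The effect on the AE listing cannot be estimated and may be zero, since no event rate is given; the panel is capped at 15 qualified subjects unless the sponsor approves more.

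This rests on two assumptions: that the two lists in Section 8.1 are read as their headings say, one of inclusions and one of exclusions, and that the investigator, who is responsible for detecting and documenting AEs under Section 8, sees the scores recorded at the 16 to 24 hour reading.

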#### Events NOT meeting the AE definition:

- Any clinically significant abnormal laboratory findings (if applicable) or other abnormal safety assessments which are associated with the underlying disease, unless judged by the investigator to be more severe than expected for the subject's condition.

#### CONFIDENTIAL

This document is a confidential communication of Consumer Product Testing Company, Inc. containing Testing Facility capabilities and processes, and as such, is intended solely for the use of the Sponsor and Testing Facility in the performance of services. The confidential information contained herein, shall only be released by either Party upon compelled disclosure in compliance with legal or regulatory requirement.

- The disease/disorder being studied or expected progression, signs, or symptoms of the disease/disorder being studied, unless more severe than expected for the subject's condition.
- Medical or surgical procedure (e.g., endoscopy, appendectomy) is not the AE. The condition that leads to the procedure is an AE (e.g., appendicitis).
- Situations where an untoward medical occurrence did not occur (social and/or convenience admission to a hospital).
- Anticipated day-to-day fluctuations of pre-existing disease(s) or condition(s) present or detected at the start of the trial that do not worsen.
- Localized erythema caused by exposure of the skin to UV radiation is expected and will not be reported as an adverse event.

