## 7 Statistical Methods

### 7.1 Rejection of Data

Test data from a qualified subject shall be invalid and rejected for any of the following reasons:

- If the exposure series fails to elicit an MED response on either the treated or unprotected test sites;
- If the responses on the treated test sites are randomly absent (which indicated the test material (or control standard) was not spread evenly);
- If all subsites on the exposure series show an erythema response upon evaluation; or
- If the subject was noncompliant (e.g., subject withdraws from the test due to illness or work conflicts; subject does not shield the exposed test sites from further UV radiation until the MED is read, etc.).

If data are rejected for any one test material on more than 5 qualified subjects, then the entire test for that material is invalid and shall be rejected. If data are rejected for the control standard (Reference Sunscreen Formulation) on more than 5 qualified subjects, then the entire test is invalid and shall be rejected.

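### Section 8.1 exempts all localized UV erythema from AE reporting with no severity limit, so redness clearly stronger than the UV dose should produce gets no AE record, AE intensity grade or required follow-up

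*Combined protocol and SAP*

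**What the plan says.** Section 8.1 lists events that do not meet the AE definition. The last bullet reads: "Localized erythema caused by exposure of the skin to UV radiation is expected and will not be reported as an adverse event". It contains no severity limit and no investigator judgment.

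Three other bullets in that list are limited:

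- Abnormal laboratory or safety findings linked to underlying disease are exempt "unless judged by the investigator to be more severe than expected for the subject's condition".
- The disease being studied is exempt "unless more severe than expected for the subject's condition".
- Pre-existing conditions are covered only as "Anticipated day-to-day fluctuations of pre-existing disease(s) or condition(s) present or detected at the start of the trial that do not worsen".

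On the reporting side, Section 8.1 makes AEs of "Unexpected or unusual reactions which occur within the test area that cannot be completely described by the scale in 6.2.2". It sends lack of efficacy as such to the efficacy assessments, but adds that "signs, symptoms, and/or clinical sequelae resulting from lack of efficacy will be reported as AE if they fulfill the definition of an AE". The scale in Section 6.2.2 runs from 0 to 4, and score 3 is "Strong erythema, edema". Section 6.3.3 has the sites read 16 to 24 hours after exposure.

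**The concern.** UV erythema is the one harm this trial causes on purpose. The exemption is needed, because without it every successful MED reading would be an AE. As written, however, it declares the whole class expected, whatever the intensity. If an irradiated site turns out much redder than its dose should make it, the text tells the investigator not to report it as an AE. Follow-up of that subject then rests on the goodwill of the site and not on a protocol duty, and the AE part of the final report would not show the event. What is at stake is subject safety and the completeness of safety reporting. The efficacy result is not at stake.

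**Working it through.** The plan gives no figure on this point and no arithmetic applies. The check is a comparison of clauses.

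**Step 1. The exemptions in Section 8.1, side by side.**

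| Exempt event | Limit |
|---|---|
| Abnormal findings tied to underlying disease | More severe than expected, by investigator judgment |
| Disease being studied | More severe than expected |
| Medical or surgical procedure | Not a clinical finding; the underlying condition is the AE |
| Social or convenience admission | Not a clinical finding |
| Fluctuation of a pre-existing condition | Must not worsen |
| Localized UV erythema | None |

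**Step 2. Can another clause bring excessive redness back in?**

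- *Test-area reactions.* The clause needs a reaction that the 6.2.2 scale cannot completely describe. Strong erythema is named at score 3, so redness alone, however disproportionate to the dose, appears to be on the scale. Score 3 couples strong erythema with edema, so one could argue that strong redness without edema is not perfectly described. The clause therefore does not clearly reach it.
- *Lack of efficacy.* Signs that result from it count only if they already meet the AE definition, which leads back to the exemption. The clause also cannot apply to the unprotected MEDu site, where no product is used.
- *General definition.* It is broad, but a specific exclusion for this finding takes precedence over it.

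**Step 3. What depends on AE status?**

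- The AE page of the CRF (Section 8.4.1) is for AEs.
- The mild/moderate/severe assessment (Section 8.5.1) is made for each reported AE.
- Follow-up until resolution or stabilization (Section 8.6) applies to AEs.
- Under Section 8.2, an event that is not an AE cannot become an SAE.

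**Step 4. What is still captured?**

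- Immediate responses go on the CRF, and each site is evaluated once at 16 to 24 hours (Section 6.3.3) on the 0 to 4 scale. No later skin check is specified.
- Section 9 requires data on subjects' experience with the regimen to go to the sponsor.
- Section 5.6 encourages safety evaluations for withdrawn subjects, but not for those who complete.
- The final report (Section 11.8) lists individual MEDs, SPFi values and AEs. It does not list erythema scores.

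Excessive UV redness is therefore seen and scored, but as an efficacy reading that triggers no safety duty.

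**The case against.** The strongest reply is that a boundary already exists in a form suited to this trial. The bullet covers only erythema that is localized and caused by UV, and anything the scale cannot describe is an AE. The limits in the neighbouring bullets concern disease, and this trial studies none and excludes subjects in ill health, so the difference in wording need not be an oversight. What remains is redness confined to the field, without pain, blistering or other sequelae.

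Much of this stands, and it is why the point is minor. It does not remove the gap. A boundary set by what the scale can describe leaves out precisely the strong redness that the scale names. One might also read the word expected as an implied limit, but the sentence asserts that UV erythema is expected; it does not exempt only the expected part.

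A second reply also stands: on protected sites, redness beyond expectation may simply be a low SPFi, which Section 8.1 sends to efficacy. Any rewording must respect that.

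Several stronger readings are tempting and should not be drawn:

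- *That the redness goes unrecorded or ungraded.* It receives a 0 to 4 score. Only the AE record, AE grade and required follow-up are missing.
- *That edema and blistering are exempt too.* The bullet names erythema only. Because the scale also lists edema and blistering, their status is less than clear, but the text does not exclude them.
- *That the data-rejection rule in Section 7.1, "If all subsites on the exposure series show an erythema response upon evaluation", shows that severe over-response is anticipated.* An all-red series may mean only that the dose range began too high; every score could be 1.
- *That AE incidence is understated by some number of percentage points.* The documents give no case count, and neither Section 7.4 nor Section 11.8 plans an AE incidence.

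**Conclusion.** The concern holds in a narrow form. Section 8.1 exempts localized UV erythema without a severity limit, and no other clause clearly restores reporting when redness in the irradiated field is clearly stronger than the dose should produce. Such a case would have an efficacy score at 16 to 24 hours but no AE record, no AE intensity grade and no required follow-up to resolution. Unusually persistent redness is ambiguous rather than plainly excluded, because neither the bullet nor the scale has a time element.

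The size cannot be put in numbers. The documents give no frequency, and it is probably low. The SPF estimate is unaffected. The conclusion assumes that the investigator applies the bullet as written and that a specific exclusion overrides the general AE definition. It is a minor point and a cheap improvement.

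**What to change.** In the Section 8.1 bullet, restrict the exemption to erythema confined to the irradiated subsites, and end it with: *unless, in the investigator's judgment, it is more severe or more persistent than expected for the UV exposure given.* Then add: *A low MEDp or SPFi alone is lack of efficacy and is not an adverse event.*

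The first addition follows the model of the limits already in the list and settles the question of duration. The second keeps the efficacy outcome from being reported twice.

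The cost is a protocol amendment to one bullet, with no new visit, procedure, staff or data field. The downside is that a few more AEs may be recorded and the investigator must judge what exceeds expectation. The subject's own MEDu and the known dose series give a benchmark for that judgment.
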